10. ANALYTICAL PLAN AND STATISTICAL METHODS

10.1 GENERAL CONVENTIONS AND STATISTICAL CONSIDERATIONS

All statistical analyses will be performed, and data appendices will be created using the SAS system version 9.4 or higher.

Data collected in this study will be presented in patient data listings and summary tables.

Descriptive statistics (number of patients with non-missing values, mean, standard deviation [SD], median, minimum, and maximum) will be presented for continuous variables. All raw data will be presented to the original number of decimal places. Means and medians will be presented to 1 more decimal place than in the raw data. Standard deviations will be presented to 2 more decimal places than in the raw data. Descriptive summaries of time to event data will include medians and confidence intervals.

All data will be listed for all patients.

Frequency distributions (counts and percentages) together with mean and SD of ordinal scores will be presented for categorical variables. Discrete variables that are ordinal scaled (e.g., Eastern Cooperative Oncology Group [ECOG] performance score) will additionally be presented with mean scores and SD. If not specified otherwise, the number of observations with non-missing values will be the denominator for percentage calculation. Further details on the handling of missing observations are given in section 9.3.

If days are converted to months, a factor of 30.4 days/month will be used. If days are converted to years, a factor of 365.25 days/year will be used. Time will be shown in study weeks, i.e., number of weeks from the first administration of any study drug.

Dose-Escalation (Part A). The dose-escalation analysis will be presented by OBI-999 dose (0.4, 0.8, 1.2, and 1.6 mg/kg) cohorts and overall. The following cohorts and overall will be presented:

- OBI-999 0.4 mg/kg
- OBI-999 0.8 mg/kg
- OBI-999 1.2 mg/kg
- OBI-999 1.6 mg/kg
- Dose-Escalation Total

OBI-999 2.0 mg/kg was planned but Part A was closed before this dose was administered, and therefore there no patients in this cohort. For this reason, this cohort will not be presented in any of the analyses.

Cohort-Expansion (Part B). The expansion part analysis will be presented by cancer type. The following cohorts and overall will be presented:

- Cohort 1: Pancreatic cancer
- Cohort 2: Colorectal cancer
- Cohort 3: Basket (any solid tumor type other than those included in Cohorts 1 and 2)
- Cohort-Expansion Total

10.2 DEFINITION OF BASELINE, STUDY VISITS, AND VISIT WINDOWS

Baseline for each assessment is defined as the last non-missing assessment prior to first dose of study drug. If scheduled and unscheduled assessments occurred on the same day and they both can qualify for being baseline, the value from the scheduled assessment should be considered as baseline. The baseline will be presented for each part.

The data will be analyzed according to the visits recorded in the eCRF. No additional visit windows will be applied. In listings, any unscheduled visits will be inserted in the appropriate temporal sequence using visit date and time.

10.3 HANDLING OF MISSING DATA

Partial or missing start and end dates of AEs and concomitant medications will be imputed conservatively based on the rule described in Appendix II: Imputation rules for missing dates. The imputed dates will be used to allocate the AEs and concomitant medications to a study period, and to determine whether an AE is/is not treatment emergent. Listings of the AEs and concomitant medications will present the actual partial dates; imputed dates will not be shown in the listings.

For ORR endpoint, patients with missing data (for any reason) will be included as non-responders in the statistical analysis for each related follow-up analysis. For analyses performed in the safety population, patients who discontinue due to toxicity or clinical progression prior to post-baseline tumor assessments will be considered as non-responders and retained in the denominator.

For CBR endpoint, patients with missing data (for any reason) will be included as non-responders in the statistical analysis for each related follow-up analysis.

10.4 PATIENT DISPOSITION

The number of patients screened and the reasons for screen failure from main consent, including

exclusion criteria met and inclusion criteria not met, will be tabulated overall in the screened population (all patients who have signed main informed consent) by Parts A and B.

Patients in each analysis population, as well as patients who complete the treatment, complete the study, and patients who prematurely discontinue from treatment and from the study, together with number of enrolled patients, will be tabulated as indicated in section 9.1. The number and percentage within each category will be presented by Parts A and B and by cohort (by dose level in Part A and by cancer type in Part B).

The number and percentage of patients included in the safety, efficacy and PK populations will also be conducted by study part and by cohort (by dose level in Part A and by cancer type in Part B).

A listing with all enrolled patients (all patients who have been screened and are eligible) will be generated for the study to describe country/study center, patient number, study part, cohort, date of Globo-H screening consent, Globo-H screening consent version, date of main informed consent, informed consent version, was informed consent withdrawn, date of withdrawal, first and last study drug dosing dates, total duration of study drug dosing, the reason for discontinuing study drug dosing, end of study (completion or discontinuation) date, and reason for discontinuing the study.

10.5 PROTOCOL DEVIATIONS

Protocol deviations will be classified as major and minor as specified in the Protocol Deviations Management Plan. Patients with major protocol deviations will be identified and documented before the database lock.

The number and percentage of patients with at least one major protocol deviation and the categories of the major protocol deviations will be summarized by study part and by cohort (by dose level in Part A and by cancer type in Part B) using the safety and efficacy populations.

The number and percentages of patients with at least one major protocol deviation related to COVID-19 will be summarized too.

Protocol deviations related to COVID-19 will be listed.

10.6 PATIENT CHARACTERISTICS

Baseline and demographic characteristics will be summarized for the screen failures population and by study part and by cohort (by dose level in Part A and by cancer type in Part B) using the safety population. Medical history, prior and concomitant medications will be summarized by study part and by cohort (by dose level in Part A and by cancer type in Part B) using the safety and efficacy populations.

10.6.1 BASELINE AND DEMOGRAPHIC CHARACTERISTICS

Descriptive statistics for continuous variables (age at screening, height at screening, weight at baseline, body mass index [BMI] at baseline, and Globo H score) and frequency counts and percentages for categorical demographic variables (child-bearing status, sex, ethnicity, race, Globo H [positive/negative] and ECOG performance) will be summarized by study part, and by

cohort (by dose level in Part A and by cancer type in Part B) using the safety and efficacy populations.

BMI will be derived as: BMI [kg/m²] = weight[kg]/(height[cm]/100)².

Height reported in inches will be converted to centimeters as: Height [cm] = height [in] * 2.54.

Baseline and demographic characteristics will be provided in a listing.

10.6.2 MEDICAL HISTORY AND CURRENT MEDICAL CONDITIONS

Medical history (conditions not ongoing at screening) and concomitant conditions (ongoing at screening or unknown) will be coded using Medical Dictionary for Drug Regulatory Activities (MedDRA®) version 23.0 or newer. The number and percentage of patients reporting a history of any medical condition, as recorded on the eCRF, will be summarized by study part, by cohort (by dose level in Part A and by cancer type in Part B), by System Organ Class (SOC) and preferred term (PT) in the safety and efficacy populations. Patients having the same medical condition (based on SOC and PT) more than once will be counted only once for a particular SOC and PT.

Medical history, disease characteristics, surgical and medical procedures will be listed.

10.6.3 PRIOR AND CONCOMITANT MEDICATIONS

Illnesses first occurring or detected during the study and/or worsening of a concomitant illness during the study will be documented as AEs on the eCRF.

All prior and concomitant medications will be coded using September 2019 Format Global B3 version of World Health Organization Drug Dictionary Enhanced (WHO-DD) and will be further classified to the appropriate Anatomical Therapeutic Chemical (ATC) code. The exact version of the dictionary is subject to change.

The number and percentages of patients with at least one prior or concomitant medication will be summarized by ATC level 4 and ATC level 2 classes and WHO-DD preferred term (PT). Prior and concomitant medications will be summarized by study part, and by cohort (by dose level in Part A and by cancer type in Part B) in the safety and efficacy populations. These summaries will be done separately.

A medication is considered prior if the end date of the medication is prior to the first study drug dose date. A medication is considered concomitant if it is administered before the first study drug dose date and is continuing at the time of the first dose of study drug, or if it is administered on or after the first study drug dose date up to 28 days after patient's last study drug dose.

Patients receiving the same medication more than once will be counted only once for a particular medication class, where applicable.

Medications having both start and end dates missing will be considered concomitant; in the case of a missing start date and not a missing end date the medication will be considered concomitant unless the end date is prior to the date of the first dose.

All prior and concomitant medications will be provided in a listing.

10.6.4 CANCER HISTORY

Location of primary tumor, histological/molecular subtype of cancer, elevation of tumor-specific serum markers observed prior to study entry, tumor marker elevated (if elevation observed), TNM stage at study entry, TNM stage at diagnosis of advanced disease, metastatic sites and previous cancer therapies will be tabulated. Data will be summarized in the safety and efficacy populations by study part, and by cohort (by dose level in Part A and by cancer type in Part B).

Cancer history will be listed.

10.6.5 OTHER MEDICAL HISTORY

Medical history terms, start/end dates, ongoing status, active treatment at study entry will be presented in a listing.

10.6.6 PRIOR CANCER SURGERIES

Prior cancer surgery description and date will be presented in a listing.

10.6.7 PRIOR CANCER RADIOTHERAPY

Radiation field (anatomic site), first and last dose dates, and total dose with units will be presented in a listing.

10.6.8 PRIOR CANCER MEDICATION THERAPY

Treatment setting, best response to treatment, and reason to stop treatment will be tabulated. Data will be summarized in the safety and efficacy populations by study part, and by cohort (by dose level in Part A and by cancer type in Part B).

Prior cancer medication therapies will be presented in a listing.

10.6.9 SMOKING HISTORY

Substance type, usage status, frequency, length of usage and smoking exposure will be tabulated; descriptive statistics for continuous variable ('Number used' eCRF field) will be summarized by study part, and by cohort (by dose level in Part A and by cancer type in Part B) using the safety and efficacy populations.

Length of usage, presented in years, will be calculated as the difference in stop and start dates of usage/365.25.

Quantification of smoking exposure will be expressed as "pack-years". Pack-years will be calculated as follows: number of years participant smoked*number of cigarettes smoked per day divided by 20. The following rules will be applied to calculate "pack-years":

- 1 pipe = 2.5 cigarettes.
- 1 cigar = 2.5 cigarettes.
- 20 cigarettes a day for 1 year = 1 pack-year.
- 8 pipes a day for 1 year = 1 pack-year.
- 8 cigars a day for 1 year = 1 pack-year.

Smoking history will be provided in a listing.

10.7 ANALYSIS OF STUDY ENDPOINTS

This section describes analysis of primary, secondary and exploratory endpoints as per protocol. All endpoints will be analyzed using planned treatments. Summaries will be presented for safety population in Part A and Part B. Summaries for anti-OBI 999 antibodies (ADA) in Part B will be presented in PK and safety populations.

Only those analyses marked with * will be analyzed in aCSR as per sponsor decision.

10.7.1 PRIMARY ENDPOINTS

PART A (DOSE-ESCALATION)

A. AEs/ SAEs and laboratory abnormalities as graded by NCI CTCAE version 5.0*.

Treatment emergent adverse events (TEAEs) are defined as AEs with onset dates on or after the start of study drug until 28 days after the last dose of study drug or if it is present prior to receipt of the study treatment but worsens in severity or increases in frequency on or after the first dose. AEs having both onset and end dates missing will be considered as TEAEs.

TEAEs will be summarized by study part, cohort (by dose level in Part A and by cancer type in Part B), SOC, PT, severity grade, and relationship to treatment. SAEs, deaths, and AEs leading to early treatment discontinuation (collected on Adverse Events eCRF page) will be summarized. The summaries will be sorted by decreasing order of overall incidence of SOCs and decreasing order of overall incidence of PTs within SOCs.

Events reported as “Unrelated” or “Unlikely related” to study drug will be considered as unrelated to the study drug. Events reported as “Possibly related”, “Probably related”, “Definitely related” to study drug or without relationship information will be considered as related to the respective treatment.

Overview summaries of the number and percentages of patients and number of events within the following categories will be provided by study part and by cohort (by dose level in Part A and by cancer type in Part B):

- Any TEAE
- Any TEAE grade ≥ 3
- Any TEAE related to OBI-999
- Any Serious TEAE
- Any Non-Serious TEAE
- Any Serious TEAE related to OBI-999
- Any TEAE leading to death
- Any TEAE leading to discontinuation of OBI-999 (defined as AE with an action taken equals to “Drug Withdrawn”)
- Any Serious TEAE leading to discontinuation of OBI-999 (defined as AE with an action taken equals to “Drug Withdrawn”)
- Any TEAE leading to study discontinuation (defined as AE flagged as Grade 4 infusion reactions and OBI-999 related toxicity, or intercurrent illness in the “End of Study” eCRF

page)

- Any Serious TEAE leading to study discontinuation (defined as AE flagged as Grade 4 infusion reactions and OBI-999 related toxicity, or intercurrent illness in the “End of Study” eCRF page)

Tables by SOC and PT will be displayed for following AEs. Only those AEs marked with * will be analyzed in the aCSR as per sponsor decision.

- TEAEs*
- TEAEs grade ≥ 3 *
- TEAEs related to OBI-999*
- Serious TEAEs*
- Non-Serious TEAEs
- Serious TEAEs related to OBI-999*
- TEAEs leading to death*
- TEAEs leading to discontinuation of OBI-999*
- Serious TEAEs leading to discontinuation of OBI-999*
- TEAEs leading to study discontinuation*
- Serious TEAEs leading to study discontinuation*

Tables by SOC and PT will display the incidence of events (number of events, number and percentage of patients with any event, number of events of each specific SOC, number and percentage of patients with any event of each specific SOC, number of events of each specific PT and number and percentage of patients with any event of each specific PT).

Tables of TEAEs and serious TEAEs by SOC, PT and worst CTCAE grade (per summarization level) will be presented and will display number and percentage of patients with any event of each specific SOC/PT/CTCAE grade. Number of events will not be displayed. If a patient has multiple AEs with the same SOC or SOC and PT respectively and one of them has missing severity, the highest severity will be used. If the severity is missing for all AEs with the same SOC or SOC and PT, a “missing” category will be added in the summary table.

The following listings will be prepared for AEs. Only those AEs marked with * will be listed in the aCSR as per sponsor decision.

- Pre-treatment AEs
- All TEAEs*
- All TESAEs*
- All TEAEs related to OBI-999*
- TEAEs leading to death (with Grade 5 or “Fatal” as an outcome)*
- All TEAEs leading to discontinuation of OBI-999*
- All TEAEs leading to study discontinuation
- Post-treatment AEs

Number and percentage of patients with laboratory abnormalities with grade ≥ 3 will be provided by study part, by cohort (by dose level in Part A and by cancer type in Part B) and by visit.

B. Dose-limiting toxicities (DLTs) with OBI-999*

A DLT is defined as the occurrence of any of the following events, within the first cycle of treatment that is considered to be at least possibly related to OBI-999:

- Grade 4 neutropenia lasting more than 7 days.
- Febrile neutropenia.
- Grade 4 thrombocytopenia.
- Grade 3 thrombocytopenia with \geq Grade 2 bleeding requiring platelet transfusions.
- \geq Grade 3 fatigue, nausea and vomiting or diarrhea for more than 72 hours despite optimal supportive care.
- Any Grade 4 gastrointestinal toxicity.
- Any \geq Grade 3 non-hematological toxicity (except Grade 3 fatigue, nausea, vomiting, or diarrhea lasting $<$ 24 hours with optimal therapy, Grade 3 non-hematologic laboratory abnormalities that resolve to Grade 1 or baseline within 14 days).

All TEAEs, unless they are determined to be not related to study drug will be taken into consideration in determining DLTs. The period for DLT observation is 21 days from the start of first dose of OBI-999 (i.e., Day 1).

DLTs (not to be programmatically derived; will be analyzed as collected on eCRF) will be displayed by dose level in a frequency table in decreasing order of incidence. AEs will be graded according to the NCI CTCAE V5.0. All TEAEs unless they have been determined to be not related to study drug will be DLTs and will be summarized by dose, SOC and PT. A listing of DLTs will be prepared.

C. MTD and RP2D of OBI-999

At the time of this version of the SAP, Part A (Dose-Escalation) was completed. The RP2D of 1.2 mg/kg was identified during SRC review.

PART B (COHORT-EXPANSION)

A. Objective Response*

Overall tumor response (not to be programmatically derived; will be analyzed as collected on eCRF) will be listed by cancer type and visit. For each patient, best overall response (BOR) is defined as the best overall tumor response (complete response [CR], partial response [PR], stable disease [SD], and progressive disease [PD], or not evaluable [NE]) from the start of treatment until disease progression, recurrence or end of study. In general, the patient's best response assignment will depend on both the tumor measurement and confirmation criteria.

If an NE response is determined at a time point, this response will be ignored and subsequent non-NE responses will be used for the confirmation. For example, the sequence of tumor assessments: PR, NE, NE, CR, SD, that had more than two consecutive NEs, the third subsequent non-NE response (CR) is used as the confirmation of the first PR for best overall response derivation.

A requirement for SD is that it should be met at least once \geq 6 weeks after the first dose of trial treatment, otherwise the best response will be NE.

The criteria for confirmation of the response are summarized in the following table (Eisenhauer

et al, 2009):

Overall response first time point	Overall response subsequent time point	Best overall response
CR	CR	CR
CR	PR	SD, PD or PR [1]
CR	SD	SD provided minimum criteria for SD duration met, otherwise PD
CR	PD	SD provided minimum criteria for SD duration met, otherwise PD
CR	NE for all subsequent time points	SD provided minimum criteria for SD duration met, otherwise NE
PR	CR	PR
PR	PR	PR
PR	SD	SD
PR	PD	SD provided minimum criteria for SD duration met, otherwise PD
PR	NE for all subsequent time points	SD provided minimum criteria for SD duration met, otherwise NE
NE	NE	NE

[1] If a CR is truly met at first timepoint, then any disease seen at a subsequent timepoint, even disease meeting PR criteria relative to baseline, makes the disease PD at that point (since disease must have re-appeared after CR). Best response would depend on whether minimum duration of SD was met. However, sometimes 'CR' may be claimed when subsequent scans suggest small lesions were likely still present and in fact the patient had PR, not CR at the first timepoint. Under these circumstances, the original CR should be changed to a PR and the best response is PR.

Objective Response Rate (ORR) is defined as the percentage of patients with confirmed PR or CR based on tumor assessment as determined by RECIST 1.1 among all the patients in the safety and efficacy populations. A confirmed response will be defined as two or more consecutive assessments separated by at least 3 weeks. For summaries in the safety population, patients who discontinue due to toxicity or clinical progression prior to post-baseline tumor assessments will be considered as non-responders and retained in the denominator. A summary with the number of patients by BOR categories, ORR and the Clopper-Pearson 95% confidence interval (CI) for the ORR will be provided.

A by-patient swim lane plot of time (weeks) to Overall Response will be provided, along with waterfall plots (bar plot) showing the best reduction in target lesion therapy will be presented for Cohort-Expansion patients.

Sample code for ORR is provided below:

```
proc freq data=data;
by cohort;
tables AVAL/binomial alpha=0.05 nocum norow;
exact binomial;
run;
```

If the BOR used for ORR based on unconfirmed and confirmed overall responses differs by 10%, then we will present the same summary for ORR based on unconfirmed overall responses as a sensitivity analysis.

B. Clinical Benefit Rate

Clinical benefit rate (CBR) is defined as the percentage of patients with confirmed CR, PR, or SD among all the patients of the safety and efficacy populations. A confirmed response will be defined as two or more consecutive assessments separated by at least 3 weeks. Patients who discontinue prior to post-baseline tumor assessments will be considered as non-responders and retained in the denominator. This analysis is similar to ORR.

If the BOR used for CBR based on unconfirmed and confirmed overall responses differs by 10%, then we will present the same summary for CBR based on unconfirmed overall responses as a sensitivity analysis.

C. Duration of Response

DOOR is defined as the time from date of confirmed PR or CR to date of progression or death due to any cause and will be expressed in months. For patients who are alive and progression-free at the time of analysis, DOOR will be censored at the last tumor assessment date. The DOOR will only be evaluated for the subgroup of patients with a confirmed PR/CR using the Kaplan Meier method.

A summary of the patients with disease progression, or death, or the number of patients censored will be presented by the median time, Q1, Q3 and survival rates along with 95% CI, minimum and maximum will be provided.

Patients who discontinue from the study without experiencing any pre-defined events or patients who completed the study period without experiencing any pre-defined events will be included in statistical analysis as censored.

Sample code for duration of response is provided below:

```
ods output Quartiles=QUARTS;
proc lifetest data=DATA method=km OUTSURV=KMEST;
by COHORT;
time AVAL*CENSOR(1);
run;
ods output close;
```

D. Progression Free Survival

PFS is defined as the time from first dose of study drug until radiographically determined disease progression or death due to any cause, whichever occurs first. Patients who are still alive or who have no progressive disease reported at analysis will be censored at the last evaluable tumor assessment date.

Patients who discontinue from the study without experiencing any pre-defined events or patients who completed the study period without experiencing any pre-defined events will be included in

the statistical analysis as censored.

A summary of the patients with progression, or death, or the number of patients censored, presenting the median time, Q1, Q3 and survival rates along with 95% CI, minimum and maximum will be provided.

DOOR and PFS summaries will be presented for safety and efficacy populations.

As additional analysis, ORR, CBR, DOOR and PFS will be summarized for patients from Part A for safety and efficacy populations.

E. Percentage of patients with anti-OBI-999 antibodies (ADAs) in blood*

The number and percentage of patients with final ADA results in the blood will be summarized. ADAs titers over time will be summarized by cancer type in Part B using descriptive statistics, including percent coefficient of variation (CV%), geometric mean, and geometric SD using safety, and PK populations. Data listings will be produced for all ADA data.

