## 7.2 Treatment Discontinuation and Withdrawal of Patients

A patient who withdraws from the study within the DLT evaluation period for reasons other than drug related AE will be replaced.

A patient may voluntarily withdraw or be withdrawn from the study treatment at any time for reasons including, but not limited to, the following:

- Progressive disease.
- Grade 4 infusion reactions and OBI-999-related toxicity.
- Dose reductions required on more than 2 occasions for toxicity related to OBI-999.
- Treatment interruption for more than 2 consecutive doses for related or unrelated reasons.
- Patient withdrawal of consent: At any time, a patient's participation in the study may be terminated at his/her request or on the basis of the Investigator's clinical judgment.
- Inter-current illness: A condition, injury, or disease unrelated to the primary diagnosis that becomes apparent during treatment and necessitated the patient's termination from the study.
- General or specific changes in the patient's condition that renders him/her ineligible for further treatment according to the inclusion/exclusion criteria.
- Protocol deviation: The patient's findings or conduct fail to meet the protocol entry criteria or fail to adhere to the protocol requirements (e.g., drug noncompliance, failure to return for defined number of visits) such that the Sponsor and the Investigator agree that the deviation necessitates premature termination from the study.
- Lost to follow-up: The patient stops coming for visits, and study personnel are unable to contact the patient.

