**Table 8-1 OBI-999 Dose Modifications for Toxicity**

Toxicity	Hold Dose	% of Full Dose after Recovery to Grade 0-1
Grade 1	Do not hold dose	100
Grade 2	Hold dose until resolution to Grade 0 or 1	75
Grade 3	Hold dose until resolution to Grade 0 or 1	75
Grade 4	Treatment should be discontinued	Not applicable

Once the dose has been reduced for toxicity and found to be well tolerated, re-escalation may be permitted at the Investigator's discretion. If a patient requires dose reductions on more than 2 occasions for toxicity related to OBI-999, the patient should discontinue from the study.

All reasons for treatment modifications should be fully explained.

The study drug dose which is not administered within the permitted window period of  $\pm 3$  days, must be skipped, and the next dose will be administered as per protocol schedule. Any skipped dose due to safety reason and if medically justified, for OBI-999 treatment related or unrelated reasons, will not be captured as a protocol deviation for this study.

Treatment interruption for more than 2 consecutive doses for related or unrelated reasons may necessitate discontinuation of study treatment.

Treatment interruption for intercurrent non-treatment related AEs will be at the Investigator's discretion and based on the well-being of the patient. All reasons for treatment interruption and

delays should be fully explained. Treatment for hematologic and non-hematologic toxicity may be implemented as clinically indicated according to institutional guidelines. Refer Table 8-2 for therapeutic antiemetic and anti-diarrheal recommendations.

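### The SAP's definition of a TEAE leading to study discontinuation omits withdrawal for repeated toxicity-driven dose reductions, so two tables kept for the aCSR can undercount

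*SAP*

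**What the plan says.** SAP 10.7.1 (Part A, item A) lists the rows of the adverse-event overview. A TEAE leading to study discontinuation is "defined as AE flagged as Grade 4 infusion reactions and OBI-999 related toxicity, or intercurrent illness in the" End of Study eCRF page, and the serious row carries the same definition. The by-SOC-and-PT tables reuse the category names without defining them again. Two of those tables, for all such TEAEs and for "Serious TEAEs leading to study discontinuation", are starred and so kept for the abbreviated report. The listing "All TEAEs leading to study discontinuation" has no star. SAP 10.7.2 sends the Part B analysis back to the same section, which it cites under its old number, 9.7.1.

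Protocol 7.2 gives nine withdrawal reasons, each with its own bullet. Two match the SAP rule: "Grade 4 infusion reactions and OBI-999-related toxicity" and the one that begins "Inter-current illness: A condition, injury, or disease unrelated to the primary diagnosis that becomes apparent during treatment". Two other bullets read "Dose reductions required on more than 2 occasions for toxicity related to OBI-999" and "Treatment interruption for more than 2 consecutive doses for related or unrelated reasons". On the first of these, the text under Table 8-1 in Protocol 8.3 says "the patient should discontinue from the study".

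TEAEs leading to discontinuation of OBI-999 are a separate SAP category. It is defined by the action taken on the AE record (drug withdrawn) and does not depend on the End of Study page.

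**The concern.** The SAP rule follows the wording of two protocol bullets closely and passes over a third that names OBI-999 toxicity as its cause. It counts a patient who leaves for an intercurrent illness. Read literally, it does not count one who leaves because drug toxicity forced more than two dose reductions.

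The omission is not neutral. In Table 8-1, Grade 2 and Grade 3 toxicity leads to a hold and then a reduced dose, and Protocol 8.3.2.1 handles Grade 2 or 3 neuropathy in the same way. Repeated reduction is therefore a route by which persistent toxicity below Grade 4 takes a patient off study. Safety and tolerability is a primary objective, and the safety review committee weighed cumulative toxicity such as neuropathy when it chose the Part B dose (Protocol 14.6). SAP 11, which records departures from the protocol, neither mentions nor explains the restriction.

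**Working it through.** The plan gives no figure to reproduce. The check sets the SAP rule against the Protocol 7.2 list, then works out what one missed patient would do to a reported rate.

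**Mapping the nine Protocol 7.2 reasons**

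| Protocol 7.2 reason | Counted by SAP 10.7.1? | Adverse-event driven? |
|---|---|---|
| Grade 4 infusion reactions and drug-related toxicity | Yes | Yes |
| Intercurrent illness | Yes | Yes |
| More than 2 dose reductions for OBI-999 toxicity | No | Yes, by definition |
| More than 2 consecutive doses interrupted | No | Sometimes |
| Change in condition making the patient ineligible | No | Possibly |
| Progression; consent withdrawal; protocol deviation; loss to follow-up (4 reasons) | No | Not as labelled |

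Two are counted and seven are not: 2 + 1 + 1 + 1 + 4 = 9. Of the seven, one is toxicity-driven by its own wording.

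**Strength of the two routes**

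- Repeated reductions: Protocol 7.2 attributes the reductions to OBI-999 toxicity, and Protocol 8.3 says the patient should leave the study. Both elements of a TEAE leading to study discontinuation are present.
- Prolonged interruption: Protocol 7.2 covers related and unrelated causes, and Protocol 8.3 says only that stopping study treatment may become necessary. It belongs in the category only if an AE caused the interruption and the patient then left the study.

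**Direction.** If these patients have their own code on the End of Study page, the rule leaves out patients who belong in the category and adds none. The error can only be downward.

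**Size per missed patient** (change = 1/n)

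- Full stage 1 cohort, n = 9 (SAP 5.4, up to 9 per cohort): 1/9 = 11.1 percentage points.
- Pancreatic cohort if it reached 9 + 2 = 11 with its two replacements (SAP 5.4): 1/11 = 9.1 points.
- Part A total, n = 22 enrolled (SAP 5.1.1), assuming all were dosed: 1/22 = 4.5 points.

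The documents do not say how many patients left for either reason. They also do not give the final size of every Part B cohort, so no Part B total is calculated.

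**The case against.** The strongest reply is that the counted reason has two parts, and the second, OBI-999-related toxicity, carries no clear grade limit. A site could record a repeated-reduction withdrawal there, and it would be counted. The End of Study page is not in the documents, so nothing proves that it offers repeated reductions as a separate choice. This stands as a condition on the finding. It does not remove it: the SAP repeats two Protocol 7.2 bullets almost word for word, which suggests that the page follows that list. If both choices exist, the count depends on which one the site picked.

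A second reply is that the events are not lost, and this is correct. They stay in the all-TEAE tables and listing. They also appear in the starred OBI-999-discontinuation tables and listing when the action taken is drug withdrawn. The patient listing in SAP 10.4, which SAP 11 does not cut, gives each enrolled patient's reason for leaving the study. A reader might infer that the undercount would be invisible because the matching listing is not starred; the SAP 10.4 listing does not support that. It gives reasons and not AE terms, however, and a listing does not correct a table count.

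A third reply is that Protocol 7.2 introduces its list as withdrawal from study treatment. That weakens the interruption route. It does not weaken the repeated-reduction route, because Protocol 8.3 words that one as leaving the study.

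**Conclusion.** The point holds as a conditional undercount in one safety category. The SAP definition omits a withdrawal reason that is adverse-event driven by definition and that the protocol treats as study discontinuation. If the End of Study page lists the Protocol 7.2 reasons separately, the two starred tables and the matching overview rows are biased low. The cost per missed patient is 11.1 points in a cohort of 9 (9.1 in a cohort of 11) and 4.5 points in Part A. These are effects of a single hypothetical patient; no affected patient is documented.

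A reader might go further and infer that the overall rate of discontinuation for adverse events is biased low, or that the rule catches only Grade 4 or acute events and misses cumulative toxicity altogether. The documents support neither. Stopping the drug for an AE has its own starred outputs, independent of the End of Study reason, and the related-toxicity reason could take in some cumulative cases. Nor should prolonged interruption be put on the same footing as repeated reductions, since it covers unrelated causes and is worded as stopping treatment.

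**What to change.** In SAP 10.7.1, extend the definition, for all and for serious TEAEs, to:

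1. the repeated-dose-reduction reason; and
2. prolonged interruption, where an AE caused it and the patient's study participation ended.

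For these patients, count only the AE or AEs that triggered the final reduction, interruption or withdrawal. Taking every AE that ever had a dose action would label earlier, resolved events as causes of leaving the study and inflate the preferred-term counts. Protocol 12.5.1 already requires the action taken to be recorded for each AE, so the trigger should be identifiable from that entry and its dates. State that the same definition applies to the by-SOC-and-PT tables and how the remaining End of Study reasons are treated, and star the matching listing.

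The cost is a short change of wording, one programming condition and one short listing. The reported rate may become slightly less favourable. No clinical rule changes.
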